Recent studies demonstrate that habit-based weight loss interventions are a novel and effective strategy to help reduce excess weight long-term (research up to 2 years). Average weight losses in adults with overweight and obesity using habit-based interventions appear to be of clinical benefit and are statistically significant when compared with control groups. However, habit-based research is scarce and further studies are required to better understand the role of habits in weight management.

Sum Sanos, is a 12-month, one-on-one coach-led, habit-based weight loss program. Health coaches meet face-to-face with participants (or video call if face-to-face is not feasible) on a monthly basis and follow-up with them via telephone on a weekly basis. The frequency of these follow-ups is aimed to establish accountability, support and maintain engagement in the program. The methodologies that form the foundation of Sum Sanos are based on evidence of key weight-loss facilitators (i.e., habit-change, self-compassion, mindful eating, setback strategies, etc.).

Seven Savvy Habits (7SH), is a one-off self-guided booklet or smartphone application which the participants will engage in for 12-months. 7SH is focused on making simple diet and exercise behaviours habitual. The intervention focuses explicitly on the recommendations of habit-formation theory; therefore, advice on repetition and context stability are provided. Research assistants in each centre provide participants with the 7SH booklet together with a simple logbook for self-monitoring of target behaviours, or the 7SH smartphone application. Previous research of a similar intervention has shown effectiveness for long-term weight loss maintenance (24-months post-intervention) and offers a low-intensity alternative to 'usual care'.

Overall research question: Is a coach-led, or self-directed habit-based intervention more effective for weight loss and weight loss maintenance: a randomised clinical trial

Research questions

1. *Primary outcome:* What is the effectiveness of a coach-led (Sum Sanos) compared with two self-directed (7SH booklet and app) habit-based interventions on 12-month weight loss outcomes in adults with overweight or obesity?
2. *Secondary outcomes:* What are the effects of Sum Sanos and 7SH on weight loss maintenance post 12-months (open-ended time frame)?
3. What are the effects of Sum Sanos on fruit and vegetable intake, physical activity levels, blood pressure, waist circumference, health-related quality of life, habit-strength, and self-regulation of eating behaviour at 3, 6, 12 and 24 months, and how do these compare with the 7SH interventions?
4. Is there a relationship between individual temperament and BMI, weight change, habit-strength, health-related quality of life and self-regulation of eating behaviour?
5. What is the relationship between the number of coach-appointments and weight loss?

Objective: The objective of this trial is to assess the effectiveness of a coach-led (Sum Sanos) compared with two self-directed (7SH booklet and app) habit-based interventions on 12-month weight loss outcomes in adults with overweight or obesity.

Hypothesis: We hypothesise that Sum Sanos will be superior for weight loss outcomes compared with 7SH booklet and 7SH app.

Study arms: Sum Sanos vs Seven Savvy Habits Booklet vs Seven Savvy Habits App

Study design: Open-ended, multi-site, 3-armed randomised controlled trial. This is a superiority trial.

Methods: participants, interventions and outcomes

Study setting: This trial will be conducted in the community on the Gold Coast, Australia. Data collection will take place at a Bond University.

Eligibility Criteria: Eligible participants will be aged between 18 and 65 years, have a BMI ≥ 27.0 kg/m², own a smartphone, able to consent for themselves and able to attend all required appointments during the intervention period. Participants will be recruited regardless of obesity-related comorbidities (e.g., cardiovascular disease and diabetes). Exclusion criteria includes participants who are pregnant, significantly ill, participating in other weight management programs, expecting to have bariatric surgery in the next 24-months, or taking medications affecting appetite, metabolism or weight.

Interventions: There are three intervention groups in this trial.

- A. Sum Sanos™ (<https://www.sumsanos.com/>) is a 12-month, one-on-one, Coach-supported program. Participants meet with a Sum Sanos™ Health Coach monthly (either in a public place or the coaches' office), for 1 hour face-to-face or video call and receive a weekly 10-minute follow-up phone call. Each month, the participant will be presented with a new module to discuss with their Coach. Module topics include: goal setting, forming new habits, breaking old habits, mindful eating and setback strategies, to name a few.
- B. Seven Savvy Habits Booklet (7SH-B) is a program which aims to increase habitual performance of 7 proven weight management strategies, such as: reducing non-hungry eating, drinking water before meals and being active for at least 30 minutes a day, to name a few. The habits are presented in the form of a booklet, and a tracking diary is provided for self-monitoring of the habits. Participant are required to try and perform as many of the 7 habits as they can, everyday for 12 months. To support participants on the program and reduce attrition, they will receive follow-up phone calls by a member of the research team (monthly for the first 3 months then once every 3 months till the end of the intervention period).

- C. Seven Savvy Habits App (7SH-A) presents the same 7 proven weight management strategies as the 7SH-B, but the habits are presented via a smartphone application, instead of a booklet. The tracking diary for self-monitoring of the habits is embedded within the app. Participants are required to try and perform as many of the 7 habits as they can, everyday for 12 months. To support participants on the program and reduce attrition, they will receive follow-up phone calls by a member of the research team (monthly for the first 3 months then once every 3 months till the end of the intervention period).

Adherence: Participants in the three intervention groups will be provided with a tracking diary for self-monitoring. Sum Sanos participants will present the diary to their coaches at their monthly meeting. They will also have weekly contact with their coach which shows increased adherence through support and accountability.

7SH participants will return their tracking diary to the research assistant during the data collection appointment at 3, 6 and 12-months. Participants will receive a follow-up phone call monthly for the first 3 months, as this is the average time it takes to acquire a new habit. They will then receive a phone call once every 3 months till the end of the intervention period.

Outcome measures:

Primary: (measured at 12-months from intervention commencement)

- Weight change (kg, %) - between group differences

Secondary: (measured at 3, 6, 12 and 24-months from intervention commencement)

- Weight change (kg, %)
- Body Mass Index (BMI)
- Waist circumference (cm)
- Blood pressure
- Health related quality of life, using SF12
- Habit strength
- Self-Regulation of Eating Behaviour
- Fruit and vegetable intake
- Hours of physical activity performed per week
- Temperament
- Number of coach sessions attended (Sum Sanos)
- Number of habits achieved on average per week (7SH-B and 7SH-A)

Other:

Longer time frames for collecting secondary outcome measures (3, 4, 5 years) are dependent on funding.

Participant timeline: See Table 1

-t₁: Eligibility screening over the phone. Study information pack and consent form sent to participant via email. Participant makes appointment time to meet with research assistant.

t₀: Baseline appointment with research assistant. Provide written informed consent and baseline measurements.

t₁: During the baseline appointment, the participant is randomly allocated to an intervention by a member of the research team and informed of their intervention allocation. 7SH participants are given instructions on how to use the booklet or app. Sum Sanos participants are contacted within 24 hours by their assigned Health Coach. Commence intervention.

t₂: 3-month data collection.

t₃: 6-month data collection.

t₄: 12-month data collection. Participants cease intervention. Qualitative interviews.

t₅: 24-month follow-up data collection.

Table 1. Participant timeline

		STUDY PERIOD						
		Enrolment	Allocation	Post-allocation				Follow-up
TIMEPOINT		-t ₁ Screening	t ₀ Baseline	t ₁ Commence intervention	t ₂ 3 months	t ₃ 6 months	t ₄ 12 months	t ₅ 24-months
ENROLMENT	Eligibility screen	x						
	Informed consent		x					
	Allocation		x					
INTERVENTION	Sum Sanos™			←	→	→	→	
	Seven Savvy Habits Booklet			←	→	→	→	
	Seven Savvy Habits App			←	→	→	→	
DATA	Data collection/outcome measurements		x		x	x	x	x
	Qualitative interviews						x	

Sample size: We aim to observe a difference between Sum Sanos and 7SH intervention groups at 12-months from baseline. Sample size calculations were based on mean weight loss and standard deviation from previous trials using a similar intervention to 7SH. Our power calculation suggests 35 participants are required in each of the 3 arms to achieve a 90% power and 5% significance criterion to detect a 4kg (SD 5.03) difference between Sum Sanos and 7SH intervention groups at 12 months. To account for 30% attrition, we will recruit 138 participants.

Recruitment: The research investigators will recruit participants through local public relations, including newspaper, television and radio advertisement and through social media. Our study timeline has allowed 3 months to recruit the required sample size. The recruitment progress will be monitored on a weekly basis. If the number of enrolled participants is not reaching key milestones, additional public relation outputs will be instigated.

Methods: assignment of interventions

Allocation: Computer generation randomisation will occur after baseline assessment to allocate participants to either Sum Sanos, 7SH-B or 7SH-A (allocation ratio 1:1:1). After a 1-week run-in period, participants will be informed of their study group allocation via telephone by the primary investigator. We will use minimization stratified on, BMI categories (overweight, obese class I, II, III), age (18-30, 31-43, 44-56, 57-65 years); and gender.

Implementation: Individuals interested in participating in the trial will email through their expression of interest using the contact details specified in the media advertisements. The primary investigator will speak with each individual over the phone to conduct initial screening against the eligibility criteria. If eligible, individuals will meet with the research assistant at the relevant university, to provide written consent and baseline measurements. Ineligible individuals will be recommended to see their local health care provider for weight management support.

One week after recruitment to the trial, the primary investigator will randomise participants into one of the three study arms using the clinical trial management software package, MASCoT (<https://mascot.org.au>). Participants will be informed of their allocation via telephone call from the primary investigator.

Participants randomised to Sum Sanos, will be distributed to Life in Balance Pty Ltd (the parent company of Sum Sanos), to assign each participant with a health coach and commence the intervention. Participants randomised to the 7SH-B and 7SH-A groups, will be managed through the central research centre at Bond University.

Blinding: Outcome assessors (research assistants) and data analysts will be blinded to group allocation. Trial participants and the primary investigator will not be blinded to group allocation.

Methods: data collection, management and analysis

Data collection: An experienced research assistant blinded to treatment allocation will be trained by the primary investigator to collect data. The data collection timeline is presented in Table 2.

Table 2. Data collection timeline

	Baseline	3 months	6 months	12 months	24 months	Open-ended
Informed consent	x					
Demographic information	x					
Height	x					
Weight	x	x	x	x	x	x
Waist circumference	x	x	x	x	x	x
Blood pressure	x	x	x	x	x	x
Temperament (24 Q's)	x					
Questionnaires	x	x	x	x	x	x
- Habit-strength (32 Q's)						
- Self-regulation of eating (5 Q's)						
- Effortful Control (19 Q's)						
- Health related quality of life (12 Q's)						
- Fruit and vegetable intake (2 Q's)						
- Exercise behaviours (1 Q)						
Qualitative telephone interview				x		

Anthropometry:

Height will be measured in centimetres using a stadiometer with integrated level. As per NHMRC standard protocol for measuring height ¹; participants will be instructed to stand with feet together and flat on the ground (no footwear), with heels, shoulder blades and buttocks touching the wall. Participants will also be asked to look straight ahead; measurement will be taken as the participant takes a deep breath in and stretch to their fullest height.

Weight will be measured to the nearest 0.1kg using calibrated digital weight scales. As per the NHMRC clinical practice guidelines for the management of overweight and obesity ¹, participants will be asked to remove any outer garments, take off their shoes and empty pockets. Participants will be instructed to stand centred on the scale with weight evenly on both feet.

Body Mass Index will be calculated using body weight in kilograms (kg), divided by height in metres squared (m)².

Waist circumference (cm) will be measured using a soft tape over light clothing. Measurements will be taken twice and the average of the two recorded. As per NHMRC standard protocol ¹, participants will be asked to remove heavy outer garments, loosen any belts and empty pockets. Participants will stand with their feet close together (about 12-15cm) with their weight equally distributed and breathing normally. Waist is defined as the point midway between the iliac crest and lower rib (approximately in line with the umbilicus). Measurement will be taken in centimetres at the end of normal expiration.

Clinical:

Systolic and diastolic blood pressure will be measured using a calibrated digital inflatable cuff on the upper arm. Whilst seated, participants will be asked to raise their arm to heart level, and rest it on a table, desk or chair. After one to three minutes, the reading will be checked again for accuracy; the average of the two readings will be recorded.

Self-reported questionnaires:

All questionnaires will be distributed to participants via a secure Qualtrics web link. They will complete the questionnaires during their data collection meetings with the research assistant, in a private room at the university or healthcare clinic. Research assistants will inform participants that they may complete the questionnaires at home if they would prefer.

Habit strength: Two questionnaires will be used to measure habit strength.

1. The self-reported, 27-item Creature of Habit Scale (COHS) includes two subscales which incorporate the general concept of habits, namely *routine* behaviour and *automatic* response². The COHS measures individual's propensity for habit in daily life and demonstrates good validity and reliability². Participants rate themselves for each question using a 5-point Likert scale (1. Strongly Disagree, 2. Mildly Disagree, 3. Undecided, 4. Mildly Agree, 5. Strongly Agree), where a higher score reflects a greater expression of habitual behaviours.

2. The strength of habit instigation (deciding to do an action), will be measured using the instigation-specific item of Self-Reported Behavioural Automaticity Index (SRBAI); ('Deciding to do behaviour X is something I do automatically'). The habitual behaviours measured in this research include:
 - Deciding to eat 5 serves of vegetables a day is something I do automatically
 - Deciding to eat 2 serves of fruit a day is something I do automatically
 - Deciding to eat mindfully (avoiding distraction and eating slowly) is something I do automatically
 - Deciding to exercise consistently is something I do automatically
 - Deciding to be more active (everyday movement) is something I do automatically

Participants rate themselves for each question using a 5-point Likert scale (1. Strongly Disagree, 2. Disagree, 3. Neutral, 4. Agree, 5. Strongly Agree), where a higher score reflects a greater habit strength for the listed behaviours. The SRBAI item is a reliable measure of habit instigation ($\alpha \geq .90$)³.

Self-regulation of eating: Eating self-regulatory capacity can help individuals to cope with the obesogenic environment and achieve, as well as maintain, a healthy weight and diet. Self-Regulation of Eating Behaviour (SREBQ) is a 5-item scale used to measure eating self-regulatory capacity. The SREBQ has strong construct validity, showing a positive correlation with general measures of self-regulation. It is also positively correlated with motivation and behavioural automaticity, and negatively correlated with food responsiveness and emotional over-eating ($p < 0.001$). Overall the SREBQ is a reliable and valid measure for assessment of eating self-regulatory capacity in adult populations⁴ (questionnaire attached).

Temperament (Effortful Control): The 19-item Effortful Control Scale - short form (EC) is a subscale from the Adult Temperament questionnaire (ATQ)⁵ which assesses an individual's capacity to exert control over their behaviour and emotions as they interact with their environment. Previous studies show, lower levels of effortful control may increase risk of hedonically motivated disinhibited eating behavior (the drive to eat to obtain pleasure in the absence of an energy deficit)⁶. The relationship between effortful control and habit change is not yet understood as little to no research has been conducted on this topic.

Health-related quality of life: The Short Form-12 (SF-12) is the most commonly used and most valid and reliable health measure for assessing health-related quality of life ⁷. The 12 questions include: 2 questions concerning physical functioning; 2 questions on role limitations because of physical health problems; 1 question on bodily pain; 1 question on general health perceptions; 1 question on vitality (energy/fatigue); 1 question on social functioning; 2 questions on role limitations because of emotional problems; and 2 questions on general mental health (psychological distress and psychological well-being) ⁸.

Fruit and vegetable intake: Following Australian dietary guidelines, fruit and vegetable intakes were measured as a count of serves, from 0 to 3+ for fruit and 0 to 5+ for vegetables ⁹. Participants are simply asked, “How many serves of fruit/vegetables, do you eat on a typical day?” ¹⁰.

Exercise: Following a similar scale to fruit and vegetable intake, physical activity will be recorded as hours of exercise performed per week (1-item); “How many hours of exercise do you do in a typical week?”.

Coach sessions attended: The number of coach sessions attended (Sum Sanos) will be recorded by the health coaches and reported back to the primary investigator at 3, 6, and 12-months.

Habits achieved: The number of habits achieved (7SH-B and 7SH-A) will be recorded by the participant and reported back to the primary investigator at 3, 6, and 12-months)

Post-intervention qualitative interview: Using a maximum variation design, a selected group of participants will be invited to take part in a post-intervention interview. Semi-structured qualitative interviews will be conducted to explore participants’ general experience on the interventions. Interviews will be audio-recorded with participants’ consent, transcribed and thematically analysed. The interviews will be modelled based on a previous study conducted by the primary investigator ¹¹.

Baseline only:

Demographic information: General demographic and medical history will be collected at baseline using the participant registration form (attached).

Temperament (BIS/BAS): Previous research reports there are two general motivational systems of temperament which underly behavior and affect: a behavioural inhibition system (BIS) and a behavioural activation system (BAS) ¹². A behavioral inhibition (or avoidance) system (BIS) is said to regulate aversive motives, in which the goal is to move away from something unpleasant. A behavioral activation system (BAS) is believed to regulate appetitive motives, in which the goal is to move toward something desired. The understanding of these systems through the BIS/BAS 24-item scale, may help to predict hedonic responses to palatable food ⁶. Furthermore, there is a scarce amount of research in how these motivational systems affect habit-development and weight.

Completion of assessment: To promote completion of the data assessments, participants will have the chance to enter into a draw to win one of three \$100 shopping vouchers (relevant to their country) at each assessment point. However, they will be informed about the prize draw after commencement of the intervention to ensure only participants who are motivated to lose weight and improve their health are

recruited to the study. The primary investigator will also implement strategies to mitigate loss of data including, sending the participants birthday messages and appointment reminders.

Data management: Data will be entered, coded and managed using the software package, MASCoT. Data will then be stored, accessed, archived or destroyed in accordance to Bond University's Research Data Management and Sharing Policy (Policy number: TLR 5.12). The policy states, data will be retained for a minimum of 5 years from the date of publication. Digital data retrieved from sites outside Bond University, will be managed and stored on the Bond University network drives which are routinely backed up, and the University's digital research repository. Such precautions include password access and 'locking' data files.

Datasets (including open, controlled, access or closed digital data and records of all primary materials) of completed reports will be archived by Bond University's Library Services in appropriate facilities and will be recorded in a durable and appropriately referenced form for ease of identification and retrieval. Confidential research data and records will be stored securely.

Statistical methods: Analysis of covariance (ANCOVA) will be used for analysis of pre-post continuous measures collected during the study. For the primary outcome of change in weight at 12 months we will use linear regression to compare change in weight from baseline to 12 months with adjustment for baseline weight. We will use a type 3 analysis of effects to test the null hypothesis of no difference between the 3 treatment groups. If there is evidence of a difference ($P < 0.05$), further pairwise comparisons between groups will be undertaken. Similar analyses will be undertaken for other continuous pre-post outcomes. Treatment effects will be reported as mean differences with 95% confidence intervals.

We plan to finalise and publish a detailed statistical analysis plan (SAP) prior to completion of data collection and before any statistical analysis is undertaken.

Additional analyses: In addition to the primary analysis outlined above we will conduct an adjusted analysis of the primary outcome to assess the impact of any potential baseline imbalances between treatment groups that may have occurred by chance. Variables to be included as covariates for this analysis include treatment site (included as indicator variables), gender and age. BMI will not be included as it is highly correlated with baseline weight which is already included in the ANCOVA regression model.

Handling missing data: We will conduct intention-to-treat analysis. To account for missing primary outcome data, we will implement multiple imputation. In an additional analysis of the primary outcome we will use a per-protocol strategy to compare treatment groups after excluding participants who did not follow the study protocol.

Methods: Monitoring

Harms: Although we do not anticipate harms in this trial, participants are provided with the contact details of the primary investigator prior to recruitment and encouraged to make contact if they experience any harms, discomforts or adverse events. Participants may also discuss harms with the research assistant during data collection appointments. They may also speak with the primary investigator (7SH groups) or health coach (Sum Sanos) during the follow-up calls. An open-ended discussion on consequential events will be discussed during the 12-month interviews.

Ethics and dissemination

Research ethics approval: Ethics approval will be sought from the Bond University Human Research Ethics Committee in Australia.

Consent: Eligible participants will be emailed the Participant Information and Consent forms straight after the initial eligibility phone call. Participants will then make a baseline appointment with a research assistant who will obtain written consent from the participants.

Confidentiality: The primary investigator will deidentify participants on eligibility using the coding feature in the software package, MASCoT. Only the study manager will have the authority to reidentify participants.

Data management will comply with the Australian Standard on personal privacy protection and will act in accordance with the National Privacy Principles of the Privacy Act.

Bond University's Research Data Management and Sharing Policy ensures that research data and records are maintained securely to prevent unauthorised access, destruction, alteration or removal, accidental or intended damage or destruction.

The University's Human Research Ethics Policy ensures all researchers implement good research data management practice in accordance with legal, statutory and ethical requirements. The researchers on this project have an obligation to respect the confidentiality of information we receive in the conduct of the research. We will only use data in accordance with the agreements with the participants as outlined in the informed consent form, which take into consideration the terms of Bond University's Human Research Ethics Committee. Any notes, reports or publications will only contain anonymous data.

Declarations of interests: [name] is the co-creator of Sum Sanos and developed the Seven Savvy Habits intervention and assisted in the design of the associated booklet and app. To limit any potential bias, blinded research assistants not involved in the study design, group allocation or data analysis will conduct the data collection and a blinded biostatistician will conduct the data analysis.

In addition, a research management committee independent of Life in Balance Pty Ltd (the parent company of Sum Sanos), will meet regularly (monthly until completion of recruitment, then every 3 months)

throughout the trial to discuss the research protocol and design. [name] may attend the committee meetings as a non-voting member. A chairman will be appointed to facilitate the committee meetings.

Access to data: In accordance with the funding body agreement, the details and outcomes of this research will be made available to the Commonwealth for use as an Innovation Connections Project case study and for other purposes relating to the Commonwealth's evaluation of the program.

Bond University owns the Intellectual Property Rights in any reports or other Material it is required to provide the Commonwealth under the funding Agreement. Bond University will have ongoing custody of data and research outputs.

Sharing the information from this research with other researchers, secondary use of information for related research, publishing the data for unrelated research and non-research purposes is not planned, however is not restricted.

Non-identifiable/anonymised data or information may be deposited in an open or mediated access repository, such as the Australian Institute for Health and Welfare, where it will be handled and released for future use, in accordance with the law and their governance obligations. This includes meeting government requirements to release information under the Information Publication Scheme (<https://www.aihw.gov.au/about-us/freedom-of-information/information-publication-scheme-ips>).

The expectations of use of this data must be in accordance with the Office of the Australian Information Commissioner, which encourages all entities to take a holistic approach to ensuring that their data use is reasonable and appropriate, compliant with the Privacy Act and considers ethical and social responsibilities

Dissemination policy: The outcomes of this project will be disseminated to the participants and the public via published reports and journal publications. All data will be de-identified.

References:

1. National Health and Medical Research Council. (2013). Clinical practice guidelines for the management of overweight and obesity in adults, adolescents and children in Australia. Canberra, Australia Retrieved from http://www.nhmrc.gov.au/files/nhmrc/publications/attachments/n57_obesity_guidelines_131204_0.pdf.

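### Research assistants are declared blinded assessors, yet 7SH participants are to hand them their diaries at the measuring visits, which reveals allocation at least for booklet participants who return one

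*Protocol*

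**What the plan says.** Three places in the Protocol describe the assessors as blinded.

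- Blinding: "Outcome assessors (research assistants) and data analysts will be blinded to group allocation". Participants and the primary investigator are not blinded.
- Data collection: "An experienced research assistant blinded to treatment allocation will be trained by the primary investigator to collect data".
- Declarations of interests, after stating that one person co-created Sum Sanos and also developed 7SH: "blinded research assistants not involved in the study design, group allocation or data analysis will conduct the data collection".

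Other places bring the same role into contact with the allocation.

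- Adherence, for the two 7SH arms: "7SH participants will return their tracking diary to the research assistant during the data collection appointment at 3, 6 and 12-months". For the third arm: "Sum Sanos participants will present the diary to their coaches at their monthly meeting".
- The opening description of Seven Savvy Habits: "Research assistants in each centre provide participants with the 7SH booklet together with a simple logbook for self-monitoring of target behaviours", or alternatively the app.
- Participant timeline, t1, which takes place during the baseline appointment with the research assistant: "the participant is randomly allocated to an intervention by a member of the research team and informed of their intervention allocation". The 7SH instructions are listed at the same point.

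Allocation and Implementation give a different account of disclosure: the primary investigator telephones the participant about a week later.

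**The concern.** The person who measures weight, waist and blood pressure is meant not to know the arm. The Protocol has that person receive a document specific to the 7SH arms at the measuring visit, including the 12-month visit at which the primary outcome is taken. The contrast it exposes, 7SH against Sum Sanos, is the one the superiority hypothesis tests.

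Participants know their arm, so assessor blinding is the main protection at the moment of measurement. It is also one of the protections offered against the declared interest. If the diary procedure is followed, a report calling the trial assessor-blinded would be inaccurate for at least part of the sample.

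**Working it through.** No formula in the Protocol is at issue. The check is a comparison of sections, followed by a count of the participants affected.

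**1. Is the person who receives the diary the blinded assessor?** Blinding equates outcome assessors with research assistants. Adherence names the research assistant as recipient, at the data collection appointment. The Protocol defines no separate unblinded assistant, no collection by someone else, no sealed return and no request that participants conceal their group. As written, the roles coincide.

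**2. Does the diary reveal the arm?**

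- 7SH booklet: Interventions describes a tracking diary supplied with the booklet. Handing it over identifies a 7SH participant.
- 7SH app: Interventions says the diary sits inside the app. Adherence nominally covers all 7SH participants but does not say what an app user hands over. Allocation is revealed only if the in-app diary is shown or returned.
- Sum Sanos: the diary goes to the coach. A visit without a diary fits Sum Sanos, but it also fits an app user with nothing physical to return or a booklet user who kept or brought no diary.

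**3. How many participants?** Inputs from Sample size and Allocation: 138 recruited, ratio 1:1:1, 30% attrition.

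- Per arm at randomisation: 138 / 3 = 46.
- Per arm at 12 months, with equal attrition across arms (an assumption): 46 × 0.70 = 32.2, about 32.
- Booklet arm only: up to 46 of 138 randomised, or about 32 of about 97 at 12 months (138 × 0.70 = 96.6).
- Both 7SH arms, if app diaries are also shown or returned: up to 2 × 46 = 92 randomised, or about 64 at 12 months (2 × 32.2 = 64.4).

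All of these are ceilings, because they suppose that every attending participant in the arm returns a diary. They apply to the 3-, 6- and 12-month visits (with less attrition earlier). No diary return is planned at 24 months.

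**4. Second route, at baseline.** The opening description has research assistants supply the 7SH materials. At t1, allocation, its disclosure and the 7SH instructions all fall within the appointment held with the research assistant. Allocation and Implementation place disclosure about a week later, by telephone from the primary investigator. The two accounts cannot both be followed. The telephone version would protect the assistant at baseline, but it changes neither the diary return nor the opening description's handout of materials.

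**5. Which measurements are exposed?** Weight is read to 0.1 kg on calibrated digital scales under a set procedure; what the assessor controls is mainly the request to remove outer clothing and shoes and to empty pockets. Waist depends on locating a midpoint and applying a tape over light clothing. Blood pressure depends on positioning and a repeat reading. The scope for assessor influence is therefore smallest for the primary outcome. The Protocol gives nothing from which to put a size on it.

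**The case against.** A reader might infer that every assessor learns every allocation: 92 participants by their diary and the remaining 46 by its absence. The documents do not support that. The app arm's diary is embedded in the app, so absence of a diary need not separate Sum Sanos from 7SH-A. Diaries are forgotten. Counts of randomised participants also overstate attendance at 12 months.

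A reader might also take Habits achieved as naming a different recipient for the diary. It does not. It says the number of habits "will be recorded by the participant and reported back to the primary investigator at 3, 6, and 12-months". A count can go to one person and the diary to another, so this is no contradiction about diaries.

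Other points on the Protocol's side:

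- The opening description does not say that the assistant who supplies materials later measures the same participant. This stands, and it is why the second route is only a possible one.
- The Protocol does not say the diary is handed over before the measurements. True, but it does not say after either, and a diary seen at 3 months can inform the same assistant at 6 and 12 months.
- Weight on calibrated scales leaves limited room for bias, and waist and blood pressure are each averaged over two readings. This stands as a limit on impact.
- Declarations of interests also lists a blinded biostatistician and an independent management committee. Diary return affects neither, so it would be wrong to say that the whole safeguard fails.

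These points narrow the scope. None explains how an assistant who receives a booklet diary at the measuring visit remains blinded.

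**Conclusion.** The concern holds in limited form. The diary procedure in Adherence contradicts the assessor blinding stated in Blinding, Data collection and Declarations of interests, and nothing else in the Protocol resolves it.

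Disclosure is clear for booklet participants who return a diary and conditional for app participants. For Sum Sanos it is only suggestive. The clear part is bounded by one arm, with the 12-month figure resting on 30% attrition spread equally across arms. The baseline route is plausible but unsettled, because the Participant timeline and the Allocation and Implementation sections disagree on when and by whom participants are told their group.

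The resulting bias cannot be quantified from the Protocol. I would expect it to be limited for weight and greater for waist and blood pressure. The case for change rests on the contradiction and on how little it costs to remove, and not on a demonstrated distortion of the primary result.

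**What to change.** - **Adherence:** change the return route so that 7SH diaries do not pass through anyone who measures outcomes. A sealed identical envelope, post or an app export to existing unblinded staff who take no measurements would do. State what app participants return. If the primary investigator is to be the recipient, first check whether that person holds the declared interest, since the diaries bear on the secondary outcome of habits achieved and the Protocol as available does not show who the holder is.
- **Opening description and Participant timeline (t1):** have existing non-assessing staff disclose allocation and give out 7SH materials and instructions, and bring the timing into line with Allocation and Implementation.
- **Data collection:** add a request that participants do not reveal their group at measuring visits.
- **If this is not done:** withdraw the assessor-blinding statements in Blinding, Data collection and Declarations of interests, and report the measurements as unblinded.

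The cost is Protocol wording and reply envelopes, with no new staff. The small downside is that some posted diaries may not come back.
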